7. PLANNED ANALYSIS

For End-Of-Text (EoT) tables, the set of summary statistics is N / Mean / SD / Min / Median / Max.

For tables that are provided for endpoints with some extreme data, median, quartiles and percentiles should be preferred to mean, standard deviation, minimum and maximum.

Tabulations of frequencies for categorical data will include all possible categories and will display the number of observations in a category as well as the percentage (%) relative to the respective treatment group (unless otherwise specified, all subjects in the respective subject set whether they have non-missing values or not).

The precision for percentages should be one decimal point, unless the denominator is smaller than 100 (in all treatment columns), in which case percentages are given in integer numbers. The category missing will be displayed only if there are actually missing values.

7.1 DEMOGRAPHIC AND OTHER BASELINE CHARACTERISTICS

Only descriptive statistics are planned for this section of the report based on the treated set.

7.2 CONCOMITANT DISEASES AND MEDICATION

Only descriptive statistics are planned for this section of the report, based on the treated set. A summary of concomitant diseases will be provided by treatment group, System Organ Class (SOC) and Preferred Term (PT).

Concomitant medications will be summarized by two groups: schizophrenia and non-schizophrenia. Both baseline and on-treatment medications will be summarized.

7.3 TREATMENT COMPLIANCE

Only descriptive statistics are planned for this section of the report. Summary statistics will be given for percent compliance along with the number (%) of patients with compliance in the categories <50%, 50% - <80%, >80% (cf. [section 5.4.2](#) for calculation of treatment compliance). Similar table with the same categories will be prepared for patient adherence obtained via [REDACTED]. A patient level listing comparing traditional treatment compliance with patient adherence from [REDACTED] will also be included to facilitate patient level insights.

7.4 PRIMARY ENDPOINT(S)

The hypothesis testing strategy for primary endpoint is described in **Section 7.2 of the CTP:**

The hypothesis for the superiority testing of the primary endpoint time to remission from APS is (HR = hazard ratio):

$H_0: HR_{BI\ 409306\ / placebo} = 1$ vs. $H_a: HR_{BI\ 409306\ / placebo} \neq 1$, where $HR_{BI\ 409306}$ is the hazard ratio for the active treatment arms (i.e. BI 409306 50 mg q.d.), over 52 weeks.

Superiority will be declared if the hazard ratio between BI 409306 vs. placebo is statistically significantly less than 1 at the two-sided type I error level $\alpha = 0.1$.

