7. STATISTICAL METHODS AND DETERMINATION OF SAMPLE SIZE

7.1 STATISTICAL DESIGN - MODEL

This is a randomised, double-blind, parallel group, multi-centre trial aiming to show superiority of BI 409306 to placebo as an early intervention in patients with attenuated psychosis syndrome. All patients will be treated for 52 weeks.

The primary objective of the statistical analysis is to determine whether BI 409306 significantly increases the likelihood of remission from APS in comparison to placebo. The Cox proportional hazards model, stratified by the baseline use of antipsychotic medication, will be used to estimate and test the hazard ratio of BI 409306 vs. placebo.

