7.2 NULL AND ALTERNATIVE HYPOTHESES

The hypotheses for the superiority testing of the primary endpoint are (HR = hazard ratio):

$$H_0: HR_{BI\ 409306\ / placebo} = 1 \quad \text{vs.} \quad H_a: HR_{BI\ 409306\ / placebo} \neq 1$$

Superiority will be declared if the hazard ratio between BI 409306 vs. placebo is significantly greater than 1 at the two-sided type I error level $\alpha = 0.10$.

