7.3.1 Primary endpoint analyses

The primary endpoint is the time to remission from APS as defined in [Section 5.1.1](#).

The equality of the hazard rates will be tested by the Wald test for the treatment effect in a stratified Cox proportional hazards model at the two-sided 10% significance level. The model includes the treatment effect and NAPLS risk score as covariates and is stratified by baseline use of antipsychotic medication. Breslow's method for handling ties will be used.

The same stratified Cox proportional hazards model will be used to estimate the hazard ratio of BI 409306 vs. placebo and the asymptotic 90% Wald confidence interval. A hazard ratio of more than one favors BI 409306. The analysis will be implemented using █® PROC PHREG. Cox proportional hazard model assumptions will be verified.

[figure not shown]
The primary analysis will be performed on the FAS for the on treatment period. The date of remission will be the visit date on which the patient taking the assessment meets the remission criteria. The time to remission is defined to be the start of treatment until remission is achieved. Although patients who discontinue study medication will be followed until the end of the trial for the primary endpoint, the data collected after treatment discontinuation will only be used for a sensitivity analysis. Patients who are lost-to-follow up will be censored for the primary endpoint at the time of their last known SOPS assessment. Patients who begin taking a new prescription or increase in dose of ongoing antipsychotics will be considered as not eligible for remission. Such patients will be censored at the start of new prescription or increase of dose of ongoing antipsychotics. Further details regarding these analyses will be included in the TSAP.

The following sensitivity analyses will be performed: (1) on the primary endpoint that includes only patients from the TS during the time of the full follow-up period and (2) excluding patients who were recruited from the enriched population prior to amendment 3.

Subgroup analyses are planned and will be pre-specified in the TSAP.

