5. ENDPOINTS(S)

5.1 PRIMARY ENDPOINT(S)

The primary endpoint is time to remission from APS within a 52 week timeframe (please see **section 5.1.1** of the CTP).

Per DSM-V, the proposed diagnostic criteria for APS are:

- A. At least one of the following of symptoms is present in attenuated form, with relatively intact reality testing and is of sufficient severity or frequency to warrant clinical attention:
 - Delusions
 - Hallucinations
 - Disorganized speech.
- B. Symptom(s) must have been present at least once per week in the last 1 month
- C. Symptom(s) must have begun or worsened in the past year
- D. Symptom(s) is sufficiently distressing and disabling to the individual to warrant clinical attention
- E. Symptom(s) is not better explained by another mental disorder, including: Depressive or bipolar disorder with psychotic features and is not attributable to physiological effects of a substance or another medical condition
- F. Criteria for any psychotic disorder have never been met.

A diagnosis of APS is defined by the presence of recent attenuated positive symptoms that meet **ALL** of 5 criteria: sufficient **severity** (criterion A), sufficient **frequency** (criterion B), **recency** of onset or worsening (criterion C), associated with sufficient distress or disability to warrant clinical attention (“**warrant attention** criterion,” criterion D), and not likely due to another disorder (“**attribution** criterion,” criterion E).

A patient in remission is defined as someone who no longer meets the severity criterion.

Remission from APS is defined as a score of <3 on all of the P1-P5 Positive Symptom items of the SOPS and maintained until the end of treatment.

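### SAP 7.4 reverses the primary decision rule: for time to remission it declares superiority when the hazard ratio is below 1, which means slower remission on BI 409306

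*SAP*

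**What the plan says.** Both documents define the same primary endpoint. SAP 5.1 states: "The primary endpoint is time to remission from APS within a 52 week timeframe". The event is a good one: "Remission from APS is defined as a score of <3 on all of the P1-P5 Positive Symptom items of the SOPS", maintained to the end of treatment.

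The protocol gives the direction consistently:

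- Section 7.1: the aim is to "determine whether BI 409306 significantly increases the likelihood of remission from APS in comparison to placebo".
- Section 7.2: "Superiority will be declared if the hazard ratio between BI 409306 vs. placebo is significantly greater than 1", at a two-sided level of 0.10.
- Section 7.3.1: the stratified Cox model "will be used to estimate the hazard ratio of BI 409306 vs. placebo", and "A hazard ratio of more than one favors BI 409306".
- Section 7.7: remission of 40% on placebo and 57% on BI 409306, giving a planning hazard ratio of 1.652.

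SAP 7.4 opens with "The hypothesis testing strategy for primary endpoint is described in" Section 7.2 of the protocol. It repeats the hypotheses (ratio BI 409306 / placebo equal to 1, against not equal to 1) and then says: "Superiority will be declared if the hazard ratio between BI 409306 vs. placebo is statistically significantly less than 1", again at a two-sided level of 0.1.

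**The concern.** A hazard ratio below 1 for remission means that patients on BI 409306 remit more slowly than patients on placebo. Read literally, SAP 7.4 labels that outcome superiority and withholds the label from a drug that speeds remission. The direction would suit a harmful event such as first psychosis, not remission.

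This sentence turns the primary result into a conclusion. Whenever the 90% confidence interval excludes 1, the protocol and the SAP reach opposite verdicts on the same data. A pre-specified success criterion should not depend on someone choosing between two documents once the result is known.

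**Working it through.** **Inputs (Protocol 7.7 and Table 7.7:1).** Remission by 52 weeks of 40% on placebo and 57% on BI 409306; 150 patients per group; two-sided alpha 0.10; 20% dropout after one year; an interim look at 67% information with two-sided alpha 0.01; 133 remissions; power 89.3%.

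**Reproducing the plan's own figures.**

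- Hazard ratio under exponential times: ln(1 − 0.57) / ln(1 − 0.40) = ln 0.43 / ln 0.60 = 1.652, as stated.
- Expected remissions with exponential dropout of 20% per year: 132.1, against 133 stated.
- Power by Schoenfeld's formula with D = 133: Φ(√(D/4) · ln HR − 1.645) = Φ(5.766 × 0.502 − 1.645) = Φ(1.25) = 89.4%. Allowing for the interim look (boundary 2.576 at 67% information, final critical value 1.651) also gives 89.4%. The table says 89.3%.

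So the published power is the probability of finding a hazard ratio significantly **above** 1.

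**Chance of declaring superiority under each rule.**

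- Protocol rule: Φ(√(D/4) · ln HR − 1.645)
- SAP rule: Φ(−√(D/4) · ln HR − 1.645)

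With D = 133:

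| True hazard ratio | Protocol rule | SAP rule |
|---|---|---|
| 1.652 (planned benefit) | 89.4% | 0.0003% |
| 1.25 | 36.0% | 0.17% |
| 1.00 | 5% | 5% |
| 0.80 | 0.17% | 36.0% |
| 0.605 (inverse of 1.652) | 0.0003% | 89.4% |

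With 133 events the protocol rule is met when the observed ratio exceeds exp(2 × 1.645 / √133) = 1.33. The SAP rule is met when it falls below 1 / 1.33 = 0.75.

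**Mirror case with its own event count.** A ratio of 1 / 1.652 = 0.605 corresponds to remission of 1 − 0.60^0.605 = 26.6% on BI 409306 against 40% on placebo. Under the same dropout this gives about 90.3 expected remissions rather than 133. The SAP rule then declares superiority with probability Φ(0.502 × √90.3 / 2 − 1.645) = Φ(0.74) = 77%.

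**Smaller trial.** SAP Section 4 reports a much smaller sample than intended but gives no number. Taking 10 to 50 remissions as an assumed range, and a true ratio of 1.652:

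| Remissions | Protocol rule | SAP rule |
|---|---|---|
| 10 | 19.7% | 0.74% |
| 20 | 30.1% | 0.28% |
| 30 | 39.4% | 0.13% |
| 50 | 55.2% | 0.03% |

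By symmetry, the protocol-rule column is also the chance that the SAP rule calls the drug superior when the true ratio is 0.605 and that number of remissions is observed.

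**Was the change intended?** SAP Section 4 lists the changes to the planned analysis: no subgroup analyses, no psychometric evaluation of the SIPS/SOPS, and no sensitivity analysis excluding patients from the enriched population. Direction is not among them. The initial SAP is dated 13 December 2017. Protocol amendment 3, of 4 October 2018, moved the primary endpoint from first psychosis to remission and changed the rule in Section 7.2 from less than 1 to greater than 1. The SAP wording matches the rule before that amendment. Carry-over is the likely cause, though that is an inference.

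**The case against.** The strongest reply is that this is a transcription slip that no informed reader would act on. The SAP's introduction says it is based on Section 7 of the protocol, and SAP 7.4 names Protocol 7.2 as its source, so by its own account the protocol rule is the intended one. Nothing in either document gives the SAP precedence. The hypotheses, two-sided p-value, estimate and confidence interval are the same under both rules, and anyone who reads Protocol 7.3.1 will interpret the estimate correctly. When the 90% interval includes 1, neither rule declares superiority and the documents agree. The figures for 300 patients describe a trial larger than the one that took place.

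Much of this stands, and it bounds the point. The damage is confined to the superiority declaration. A truly helpful drug retains a small chance of meeting the SAP rule by accident (below 5%; about 1.4% at a true ratio of 1.1 with 133 events), so success under that rule is not strictly impossible. The planning figures need the caveat about sample size.

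None of it makes the sentence right. It is current text in the final SAP of 21 May 2021, it concerns the primary endpoint, and it contradicts its own cited source.

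**Conclusion.** The decision rule in SAP 7.4 is wrong as written. With remission as the event and the ratio taken as BI 409306 over placebo, benefit is a hazard ratio above 1, and an observed ratio above 1 can never satisfy the SAP criterion.

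At the planning effect the chance of declaring superiority falls from 89% to about 3 in a million. A drug that delayed remission by the same factor would be declared superior with probability about 77% at the roughly 90 remissions then expected. These figures assume exponential times, the normal approximation to the log hazard ratio, and the protocol's planned size. Their magnitude shrinks with fewer events; the reversal does not depend on them.

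**What to change.** In SAP 7.4, replace *less* by *greater* in the superiority sentence, and add that for time to remission a hazard ratio above 1 favours BI 409306, in line with Protocol 7.2 and 7.3.1.

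Add one sentence to SAP 7.5.2. Time to first episode of psychosis is analysed by the method described for the primary endpoint, but there the event is harmful and a ratio below 1 is the benefit. Stating this keeps the corrected direction from being carried across.

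The cost is one word and two clarifying sentences; no analysis, dataset or program output changes. The documents do not show whether the treatment code had been broken. If it has not, amend the SAP before it is. If it has, record the change as a correction back to the rule already pre-specified in Protocol 7.2.

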7.4.1 Sensitivity Analyses

The following sensitivity analyses will be conducted: (1) on the primary endpoint that includes only patients from the TS during the time of the full follow-up period and (2) Patients who have █ adjusted adherence over 80%.

7.5 SECONDARY ENDPOINT(S)

7.5.1 Key secondary endpoint(s)

This section is not applicable, as no key secondary endpoint has been specified in the protocol.

7.5.2 (Other) Secondary endpoint(s)

Secondary endpoints will be analyzed as described in **section 7.3.2 in the revised CTP**:

Time to First Episode of Psychosis:

Time to event endpoint will be analyzed using Cox proportional hazard model as described for the primary endpoint analysis.

Change from baseline SCoRS (at time points 24 weeks, 52 weeks respectively), BAC App (composite T score), PANSS (positive items score, negative items score and total score respectively):

All change from baseline endpoints specified in [Section 5.2.2](#) will be analyzed using the restricted maximum likelihood (REML) based mixed effects model with repeated measurements (MMRM). The model will include the fixed, categorical effects of treatment, visit, treatment by visit interaction, and baseline NAPLS risk score, and baseline use of antipsychotic medication, as well as the continuous fixed covariates of baseline score and baseline-by-visit interaction. The unstructured covariance structure will be used to model the within-patient errors. If this analysis fails to converge, compound symmetry covariance structure might be used. The Kenward-Roger approximation will be used to estimate the denominator degrees of freedom. Analyses will be implemented using █® PROC MIXED. The primary treatment comparisons will be between the placebo and BI 409306 with respect to the mean change from baseline. Adjusted mean change from baseline as well as treatment contrasts will be presented together with the 95% confidence intervals.

7.7 EXTENT OF EXPOSURE

Exposure will be analyzed on the treated set. Extent of exposure will be summarized using descriptive statistics for days of exposure as well as number (%) of patients whose total exposure falls in the categories specified in [section 5.4.2](#).

7.8 SAFETY ANALYSIS

All safety analyses will be performed on the treated set. Analyses are specified in **section 7.3.4** of the CTP.

7.8.1 Adverse events

Unless otherwise specified, the analyses of adverse events will be descriptive in nature. All analyses of AEs will be based on the number of subjects with AEs and NOT on the number of AEs.

The analysis of adverse events will be based on the concept of treatment emergent adverse events. That means all adverse events with an onset between start of treatment and end of the on-treatment period, which is 7 days after the last dose of trial medication, will be assigned to the treatment period for evaluation. All adverse events occurring before first drug intake will be assigned to 'screening' and all adverse events occurring after the residual effect period will be assigned to 'post-treatment' (for listings only).

According to ICH E3 (5), AEs classified as 'other significant' need to be reported and will include those non-serious and non-significant adverse events with:

- (i) 'action taken = discontinuation' or 'action taken = reduced', or
- (ii) marked haematological and other lab abnormalities or lead to significant concomitant therapy as identified by the Clinical Monitor/Investigator at a Medical Quality Review Meeting.

An overall summary of adverse events will be presented. The frequency of subjects with adverse events, and will be summarized by treatment, primary system organ class and

preferred term. Separate tables will be provided for subjects with other significant adverse events according to ICH E3 (5), for subjects with adverse events of special interest (only if defined) and for subjects with serious adverse events.

The system organ classes and preferred terms (within system organ class) will be sorted by frequency.

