After the individual patient's end of the trial the Investigator does not need to actively monitor the patient for AEs but should only report relevant SAEs and relevant AESIs of which the Investigator may become aware of by any means of communication, e.g. phone call. Those AEs should be reported on the BI SAE form, but not on the CRF.

The rules for Adverse Event Reporting exemptions still apply, please see [Section 5.3.6.3.](#)

The REP is defined as 7 days after the last dose of trial medication is taken. All AEs which occurred through the treatment phase and throughout the REP will be considered as on treatment, please see [Section 7.3.4.](#) Events which occurred after the REP will be considered as post treatment events.

AE reporting to sponsor and timelines

The Investigator must report SAEs, AESIs, and non-serious AEs which are relevant for the reported SAE or AESI, on the BI SAE form via fax immediately (within 24 hours) to the sponsor's unique entry point (country specific contact details will be provided in the ISF). The same timeline applies if follow-up information becomes available. In specific occasions the Investigator could inform the sponsor upfront via telephone. This does not replace the requirement to complete and fax the BI SAE form.

With receipt of any further information to these events, a follow-up SAE form has to be provided. For follow-up information the same rules and timeline apply as for initial information.

Information required

For each AE, the Investigator should provide the information requested on the appropriate CRF pages and the BI SAE form. The Investigator should determine the causal relationship to the trial medication.

The following should also be recorded as an (S)AE in the CRF and SAE form (if applicable):

- Worsening of the underlying disease or of other pre-existing conditions
- Changes in vital signs, ECG, physical examination and laboratory test results, if they are judged clinically relevant by the Investigator.

If such abnormalities already pre-exist prior to trial inclusion they will be considered as baseline conditions.

All (S)AEs, including those persisting after an individual patient's end of trial must be followed up until they have resolved, have been sufficiently characterised, or no further information can be obtained.

Pregnancy

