7.7 DETERMINATION OF SAMPLE SIZE

Remission rate of the population diagnosed with APS and without intervention was assumed to be 40% ([R16-0991](#)) by 52 weeks. The rate of remission for BI 409306 was assumed to be 57% by 52 weeks. This will lead to a hazard ratio of 1.652.

Other study considerations are:

- Two-sided alpha = 0.10
- Dropout = 20% after one year
- Interim analysis checking for early efficacy using user-defined alpha-spending boundary of 0.01 at the 67% information point

Table 7.7: 1 Power calculations for sample size (for both arms combined) of 300 for various remission rates for BI 409306 with fixed placebo group aggregate first remission rate prediction of 40% by 52 weeks

Remission Rate for Placebo	Remission Rate for BI 409306	Hazard Ratio	Risk Ratio	Power for N=300	# Events needed in total
40%	52%	1.437	1.300	64.9%	126
40%	55%	1.563	1.375	81.5%	130
40%	57%	1.652	1.425	89.3%	133
40%	59%	1.745	1.475	94.4%	136
40%	61%	1.843	1.525	97.4%	139

[Table 7.7: 1](#) displays the power achieved for 300 total randomized patients given a group aggregate first remission rate of 40% for placebo with two-sided $\alpha = 0.10$ and a user-defined

alpha spending boundary at interim analysis of $\alpha=0.01$ (two-sided). Group remission rates for BI 409306 treatment of 52%, 55%, 57%, 59% and 61% are considered. Total number of events needed to achieve the power reported is also shown.

Given remission rates of 40% for patients treated with placebo and 57% for patients treated with BI 409306, the risk ratio is 1.425 (implying that patients treated with BI 409306 will have 42.5% more chance of achieving remission of APS compared to placebo). A sample size of 300 (or 150 per group) was selected as the most logical for establishing proof of concept based on the risk / benefit considerations noted above. In addition this was the sample size used in the previous protocol and is kept the same. This translates to 89% power. The type I error was selected to be 10% since this is a phase II study meant to provide an understanding of the effectiveness of the drug without being too strict as in a confirmatory setting.

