6. GENERAL ANALYSIS DEFINITIONS

6.1 TREATMENT(S)

As described in **Section 3** of the CTP, patients will be randomized in equal allocation to one of two treatment dosage groups (50 mg and placebo) for analysis purposes.

For randomization purposes 2 arms have been defined:

- BI 409306 50 mg q.d. for 52 weeks.
- Placebo for 52 weeks.

Table 6.1: 1 Treatments and their labels per randomization list

Treatment	Short label
BI 409306 50 mg q.d.	BI 409306 50 mg
Placebo	Placebo

The trial consists of a 28 day screening period, followed by a 52 week treatment period (after randomization), and a 28 day residual effect period for follow-up.

For analysis purposes two periods have been defined in **section 7.3.1** of the CTP:

- Full follow-up
This is the entire study period, beginning with randomization until the end of the follow-up period (or date of last contact), including the residual effect period.
- On-treatment
This includes the time period from treatment start date until drug discontinuation + 7 days.

Patients who discontinue early will be followed up according to the **section 3.3.4.1** of the CTP.

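### Adverse events are summarised only as crude percentages over a window that varies by patient; a first-event rate per patient-year would guard against unequal drug stopping

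*SAP*

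**What the plan says.** SAP 7.8.1 sets the counting unit: "All analyses of AEs will be based on the number of subjects with AEs and NOT on the number of AEs". An event belongs to the treatment period if it occurs "with an onset between start of treatment and end of the on-treatment period, which is 7 days after the last dose of trial medication". After that, "all adverse events occurring after the residual effect period will be assigned to" a post-treatment class that appears in listings and not in tables. SAP 7 takes percentages over all subjects of the treatment group in the relevant set, and SAP 7.8 names the treated set for safety.

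Exposure has its own section, SAP 7.7: "Extent of exposure will be summarized using descriptive statistics for days of exposure", with categories defined in a section that is not visible. No visible text divides event counts by time at risk or plans a time-to-first-event summary. Protocol 7.3.4 describes the safety analysis as descriptive, without hypothesis tests, and refers to the sponsor's standard tables without giving their content.

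The residual effect period has two lengths. Protocol 5.3.6.2 says: "The REP is defined as 7 days after the last dose of trial medication is taken". Protocol 7.3.4 also uses 7 days. SAP 6.1 describes "a 28 day residual effect period for follow-up".

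**The concern.** Each patient's window closes shortly after that patient's last dose, but the denominator treats every patient as if observed for the same time. A patient who stops at week 4 contributes about five weeks of risk and still counts fully in the denominator of every row. If stopping is unequal, the arm with more of it has less time in which an event can be counted, and its percentage falls for a reason unrelated to safety.

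Unequal stopping is plausible but not established. Protocol 3.3.4.1 withdraws patients from treatment for adverse events and for defined suicidality, and either could depend on treatment. In the earlier schizophrenia trial described in Protocol 1.2, the share of patients with any adverse event ranged from 33.3% at 10 mg to 53.5% at 100 mg. On the other side, Protocol 2.3 reports that the 10, 25 and 50 mg groups of that trial were in the range of placebo. At stake is a modest excess of later-onset events on drug that the crude tables could show as near equality.

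**Working it through.** **The plan's own figure.** The documents give no adverse event rate. The only stated result that uses dropout is the sample size in Protocol 7.7 ("Dropout = 20% after one year", 150 per arm, remission 40% and 57%, 133 events, 89.3% power). With exponential hazards over one year:
- Dropout: −ln(0.80) = 0.2231. Remission: −ln(0.60) = 0.5108 on placebo and −ln(0.43) = 0.8440 on BI 409306.
- Expected events: 150 × (0.5108/0.7340) × (1 − 0.480) + 150 × (0.8440/1.0671) × (1 − 0.344) = 54.3 + 77.8 = 132.1, against 133 stated.
- Schoenfeld power at 133 events: z = (√133/2) × ln(1.652) − 1.645 = 1.25, or 89.4%, against 89.3% stated.

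The exponential dropout model therefore reproduces the plan's figures. It is used below as a stand-in for drug stopping, which the documents do not quantify.

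**Crude percentage at equal hazards.** Assumptions, not document figures: event hazard r = 0.5 per year in both arms, stopping independent of events, and the 20% split as 30% on active and 10% on placebo. With d = −ln(1 − stopping):

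crude = r/(r + d) × (1 − exp(−(r + d)))

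- Active, d = 0.3567: 0.5/0.8567 × (1 − 0.4246) = 33.6%.
- Placebo, d = 0.1054: 0.5/0.6054 × (1 − 0.5459) = 37.5%.
- Ratio 0.895, difference −3.9 points. The 7-day tail changes these to 34.2% and 38.1%, ratio 0.898.

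**Hidden excess.** Solving for the active hazard that gives 37.5% at 30% stopping yields 0.577, so a true hazard ratio of 1.15 would appear as equality.

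| Assumed stopping, active / placebo | Crude ratio at equal hazards | True hazard ratio shown as equality |
|---|---|---|
| 20% / 20% | 1.00 | 1.00 |
| 25% / 15% | 0.95 | 1.07 |
| 30% / 10% | 0.90 | 1.15 |
| 40% / 10% | 0.84 | 1.26 |

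The last row averages 25%, so it lies outside the planned 20%.

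**Second set of assumptions.** Take a 52-week event risk of 30% under full exposure and stopping of 40% on active versus 20% on placebo, with the 7-day tail. The crude figures are 24.4% and 27.6%, ratio 0.88. First events per patient-year are 0.357 in both arms. Over event risks of 10% to 70% the crude ratio stays between 0.88 and 0.90.

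**Early-onset events.** Put the whole 30% risk in the first month, equal in both arms. At 30% versus 10% stopping the crude figures are 29.8% and 29.9%, ratio 0.99. The first-event rate per patient-year now has a ratio of 1.12, because the arm with more stopping accrues less event-free time later. At 40% versus 10% that ratio is 1.19.

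**Boundary.** SAP 7.8.1 ends the on-treatment period at day 7 after last dose but starts the post-treatment class after the residual effect period. If that period is 28 days, as in SAP 6.1, events on days 8 to 28 fall in neither class.

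**The case against.** The strongest reply is that nothing in the documents shows unequal stopping. Protocol 7.7 gives one pooled dropout figure, as a sample-size input for remission; every split above is assumed, and equal stopping removes the distortion. That stands, and it makes the point conditional.

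A reader might infer that poor tolerability hides its own events. It does not. An event that causes stopping occurs before the window closes and is counted, and non-serious events leading to discontinuation have a separate table in SAP 7.8.1. With a true hazard ratio of 1.5, a 30% placebo risk and 20% other stopping in each arm, the crude figures are 38.1% and 27.6%, so the excess stays visible. What is lost is any later, different event in patients who stopped.

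A reader might also take the subjects-not-events rule as the fault. It is compatible with a first-event rate; the source is the variable window without person-time. Nor are the adverse event tables the only safety output. Protocol 7.3.4 plans a suicidality summary over any post-baseline visit, exposure is reported, and the data monitoring committee reviews safety imbalance. The sponsor's standard on summarising adverse events, cited in SAP 8, cannot be seen and might contain a rate.

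Size also matters. The 3.9-point gap compares with a 95% half-width of 1.96 × √(0.336 × 0.664/150 + 0.375 × 0.625/150) = 10.8 points at 150 per arm. SAP 4 says the trial is much smaller than intended; at an assumed 25 per arm the half-width is about 26.5 points.

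Finally, the remedy has its own bias: for early events such as the visual ones described in Protocol 1.2, the rate can show a false excess in the arm with shorter exposure. This stands and limits where the rate should be used.

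**Conclusion.** The point holds in conditional form. The visible plan compares adverse events only as crude percentages over a window of varying length. If drug stopping differs by arm and event risk continues through the year, the arm with more stopping can look better at equal hazards. The ratio is about 0.90 at the assumed 30% versus 10% stopping and 0.5 per year, and 0.84 to 0.95 over the other unequal splits in the table. These figures assume a constant hazard and stopping independent of events. The documents do not support the stronger reading that the safety comparison is in fact biased in favour of BI 409306, because they give no stopping by arm. For the expected early visual events the crude percentage is nearly unbiased. Severity is low: this is a supplementary descriptive analysis. The two lengths of the residual effect period are a separate inconsistency that does not depend on any assumption.

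**What to change.** In SAP 7.8.1, keep the crude percentages and add beside them the number of patients with a first event per 100 patient-years at risk, by arm, with time at risk ending at the first event or the end of the on-treatment window. Apply this to the overall, serious and special-interest summaries, and to common system organ class and preferred terms that are not concentrated shortly after first dose. State that the rate assumes a roughly constant hazard, can overstate early-onset events in the arm with shorter exposure, and is to be read with the crude percentage. Specify it before the treatment codes are released, so that it is not prompted by an observed exposure imbalance.

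Reconcile the 7-day period in Protocol 5.3.6.2, Protocol 7.3.4 and the SAP 7.8.1 window with the 28-day period in SAP 6.1, so that every event after last dose falls in one class.

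The cost is one extra column in a few tables, from data already collected, plus a wording correction.
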